The rationale for amending that protocol relates to the reported premature initiation of Phenobarbital as adjunct therapy. Most protocols call for the initiation of adjunct therapy when first line medication fails (i.e. reaching maximal doses or requiring multiple re-escalations of dosing). In Table 1 however, phenobarbital initiation happens instead during the weaning process. Accordingly, a rather large number of infants get started and discharged home on phenobarbital (22.6%).

Our goal is to introduce second-line treatment when truly indicated (i.e. when maximal safe therapy fails) and to minimize discharge home on medication, as this approach, while minimizing the LOS, allows for infants to remain on medication for an indeterminate length of time.

Principal Investigator: [name], MPH

Application Number: IRB00107690

Demonstration Study Methadone Protocol

Initiation:

Initiate protocol for infants with 2 consecutive Finnegan scores > 8. Starting dose is 0.1 mg/kg/dose Q 6 hours (Table 2 - Step 1). As per hospital policy, medications may be given +/- 1 hour from scheduled administration time

Weaning:

Table 2. Initiation and weaning of methadone			
Step	Methadone Dose (mg/kg)	Interval	Minimum Number of Doses
Step 1	0.1	Q6 h	8
Step 2	0.07	Q12 h	2
Step 3	0.05	Q12 h	2
Step 4	0.04	Q12 h	2
Step 5	0.03	Q12 h	2
Step 6	0.02	Q12 h	2
Step 7	0.01	Q12 h	2
Step 8	0.01	Q24 h	1

Initial weaning: wean after 48 hours of stable scores (i.e. 2 consecutive 24 hour Finnegan score averages < 8)
Subsequent weaning: Wean to the next step if the 24 hour Finnegan score average is < 8;
If the 24-hour Finnegan score average is 8-10, do not wean;
If the 24-hour Finnegan score average is ≥ 11, follow escalation below.

Table 2 Escalation:

- Escalation will take place by going back one step in the dosing regimen (i.e. go from Step 5 to Step 4, etc.)
- If infant needs escalation from Step 2 to Step 1, one may consider either going back up the one step to Step 1 or giving an additional methadone dose.
- Weaning will resume after 24 hours of stable scores (i.e. a 24 hour average of <8)
- If infant fails Step 1 above, increase interval of dosing to Q 4 hour (Step 1A in table 3 below)

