If infant has 2 consecutive Finnegan scores that indicate severe withdrawal symptoms, despite non-pharmacological intervention, the PI or a co-Investigator needs to be informed. The PI or a co-investigator physician will assess each situation based on infant's medication dosage, its frequency and timing of administration, and one of the 3 following options will be offered: 1) re-escalate to the previous step; 2) consider giving an additional dose of methadone if > 4 hours before the next scheduled dose and 3) consider moving up the next scheduled dose without escalation.

Principal Investigator: [name], MPH

Application Number: IRB00107690

Weaning after Step 1 escalation (steps 1A through 1C)

Table 3. Methadone escalation after weaning failure			
Step	Methadone dose (mg/kg)	Interval	Minimum Number of doses
Step 1A	0.1	Q4 h	6
Step 1B	0.1	Q8 h	3
Step 1C	0.1	Q12 h	2

Weaning: Wean to the next step if the 24 hour Finnegan score average is < 8;
If the 24-hour Finnegan score average is 8-10, do not wean;
If the 24-hour Finnegan score average is ≥ 11, follow escalation below

Table 3 Escalation:

- If patient's dosing interval has to be escalated to table 3, weaning will follow as delineated in the table.
- If infant needs escalation from Step 1B to Step 1A, one may consider either going back up the one step to Step 1 or giving an additional methadone dose.
- Once infant weans to Step 1C, further wean will be to table 2, Step 2. Weaning will then follow the protocol for table 2.

Slight variation in timing of drug administration is inherent in the provision of medical care. JHACH policy allows for drugs to be administered by nursing staff within +/- 1-hour of the scheduled timing.

Differences between Table 1 and Table 2:

As mentioned above, this modified protocol allows for initiation and weaning indications that are more in line with the AAP recommendations and the JHACH culture of minimizing infant's discomfort and providing medication weaning in a safe and conservative fashion (Table 2).

The differences between tables 1 and 2 pertain to the following:

- 1) Finnegan scores that initiate treatment: 2 consecutive scores > 8 instead of 3 scores of ≥ 8
- 2) 24-hour Finnegan score averages to guide weaning, observation and re-escalation:
 - wean if the average is <8
 - observe if average 8-10, instead of 8-12
 - re-escalate for average ≥ 11 instead of ≥ 12

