It is standard of care for infants discharged from the JHACH NICU to see their primary care provider (PCP) within a day or two of discharge. Follow-up will be provided by an IRB approved study team JHACH Pediatrician, and will take place within one or two days after discharge then weekly for 4 weeks after discontinuation of methadone treatment.

G. Off-treatment Criteria:

Principal Investigator: [name], MPH

Application Number: IRB00107690

Off-treatment is defined as an infant who no longer qualifies for discharge home on methadone – i.e. requiring adjuvant pharmacological therapy or re-admission to the hospital while still on methadone

1. Addition of adjuvant therapy:

It is common for infants suffering from NAS to require the addition of an adjunct therapeutic agent for control of symptoms. This second-line agent varies among institutions but consists often of phenobarbital.

If demonstration project participants have uncontrolled NAS symptoms (defined as a 24-hour Finnegan score average ≥ 11 despite comfort measures and maximal methadone dosing – i.e. 0.1 mg/kg given every 4 hours), the infant will be placed on phenobarbital, the standard of care at JHACH NICU. Such infant will be off-treatment from the study i.e. will not qualify for subsequent discharge home prior to discontinuation of methadone. Maternal assessments of bonding and depression will remain ongoing. There will be no home nursing visits.

2. Re-admission to the JHACH NICU:

It is common for infants suffering from NAS not to tolerate weaning off medication. Re-escalation during that phase is common. If during the weaning phase, infant's Finnegan scores are > 8 on 2 consecutive scores despite comfort measures, the dose of methadone will be increased to the previous dose at which the patient's symptoms were well controlled.

If an infant requires consecutive re-escalation of medication with no control of symptoms (i.e. 24 hour Finnegan scores > 6), such infant will be re-admitted to the hospital.

- for infants who were discharged home on a dose of methadone that is < 0.04 mg/kg, such infant will be re-admitted to the hospital if consecutive re-escalation of methadone are required and infant reaches a dose of 0.05 mg/kg.

- for infants discharged home at a dose of 0.04 mg/kg, who do not tolerate weaning at home and who require dose escalation, the dose will be increased in 2 increments per protocol to a value of 0.07 mg/kg before re-admission to the hospital.

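### Off-methadone monitoring runs 72 hours in section E but 48 hours elsewhere, so the third day's scoring is not scheduled; two related titration rules also need aligning

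*Combined protocol and SAP*

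**What the plan says.** **Monitoring after the last dose.** Section E (home observation after discontinuation) sets 72 hours off medication with nurse visits twice a day. Treatment counts as successful if the 24-hour average stays below 8, and rebound is a 24-hour average above 8. If comfort measures then fail and two consecutive assessments 3 to 4 hours apart remain above 8, methadone restarts at the last dose given. Section E calls this period important and in line with the hospital's standard of care. In the Schedule of Events for the methadone group, footnote b (home visits and Finnegan scoring) and footnote c (teleconferencing) both stop 48 hours after total weaning. Items f and h of the services list say the same. Item j adds one home visit 2 to 3 days after treatment ends.

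**Wait after re-escalation.** The Table 2 escalation bullets let weaning resume after 24 hours of stable scores. Item 3 of the list of differences between Tables 1 and 2 gives 48 hours, expressly for infants in Table 2.

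**When to raise the dose.** Table 2 works on the 24-hour average. Below 8, the infant moves down a step. For the middle band the rule is "If the 24-hour Finnegan score average is 8-10, do not wean". From 11 upwards, the infant is escalated. The differences list describes the middle band as "observe if average 8-10, instead of 8-12" and the upper one as "re-escalate for average ≥ 11 instead of ≥ 12". Section C applies the weaning protocol at home. Section G.2, on re-admission, works on individual scores. Its trigger and action read "Finnegan scores are > 8 on 2 consecutive scores despite comfort measures, the dose of methadone will be increased to the previous dose". The target is the last dose that held symptoms in check. A separate physician pathway under Table 2 begins "If infant has 2 consecutive Finnegan scores that indicate severe withdrawal symptoms, despite non-pharmacological intervention" and offers three options, of which going back a step is one.

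**The concern.** The main worry is the third day off drug. Section E's rebound definition needs enough scores to form a 24-hour average, and its restart rule needs two scores 3 to 4 hours apart. The only scheduled activity that produces scores at that spacing at home is the teleconference, and every text that schedules it stops at 48 hours. An infant who rebounds between 48 and 72 hours could be missed, or recognised late, at a time when drug may still be clearing.

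The other two points concern consistent dosing. Two nurses reading different pages could wait 24 or 48 hours before weaning again. At home they could also differ on whether two high scores call for a step up now, a call to the physician, or a wait for the daily average. In an unblinded, non-randomised study of a regimen, it should be clear which regimen was delivered.

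**Working it through.** No figure in the plan needs reproducing. The check sets the texts side by side and counts.

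**1. Third day off drug (48 to 72 h).** Inputs: visits twice daily (section E, footnote b, item f); teleconferences every 3 to 4 hours (footnote c, item h); one visit at 2 to 3 days (item j).
- Visits in total: 48/12 = 4 under the schedule and item f; 72/12 = 6 under section E.
- Teleconference scorings per 24 h: 24/4 = 6 to 24/3 = 8. This is nominal, because item h says that off drug the scoring is done when the infant is awake and feeding.
- Scores per day up to 48 h: 6 to 8 remote, plus 2 at visits if counted separately, so 6 to 10.
- Scheduled scores from 48 to 72 h: 2 under section E; 0 or 1 (item j) under the schedule and services list.

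Section E's 3-to-4-hour assessments are conditional on rebound already being suspected. Two visits a day cannot supply that spacing, and section E does not say who makes the assessments. Section C's sentence on remote scoring points back to the earlier description, which stops at 48 hours.

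The background section gives a methadone half-life of 19 ± 14 h in pediatric patients. Assuming simple first-order decline from the last dose, the fraction left at 48 h is 0.5^(48/19) = 0.17 for 19 h and 0.5^(48/33) = 0.36 for 19 + 14 = 33 h. This is illustrative only, but late rebound is not implausible.

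**2. Wait after re-escalation.** 48 − 24 = 24 h. That is 24/12 = 2 doses more or fewer at the re-escalated step for Steps 2 to 7 (every 12 h), or 24/6 = 4 at Step 1 (every 6 h).

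**3. G.2 beside Table 2, for steady scores where comfort measures have failed.**

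| Steady score | Table 2 (24-h average) | G.2 (two scores > 8) |
|---|---|---|
| 7 | wean | no trigger |
| 8 | do not wean | no trigger |
| 9 or 10 | do not wean | increase |
| 11 | escalate | increase |

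The rules give different actions only at 9 and 10. Scores alternating between 7 and 10 average (3×7 + 3×10)/6 = 8.5 and never meet G.2. Two 9s among four 7s average (2×9 + 4×7)/6 = 7.67, which reads as wean under Table 2 and increase under G.2. The two collide only if the 9s close the averaging window. If they fall earlier, G.2 acts at the second 9 and the re-escalation wait then governs.

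The choice affects dose. One step up from Step 4 takes 0.08 to 0.10 mg/kg/day (+25%), and one step up from Step 7 takes 0.02 to 0.04 (+100%).

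**The case against.** On monitoring, section E is the dedicated rule, with its own rationale. A team that follows it to 72 hours also satisfies the 48-hour visit requirement, so a safe reading of the visits exists. It also mentions 3-to-4-hour assessments itself. The first part stands for the visits. It does not rescue the scoring, because no text extends the teleconferences past 48 hours. Item j is one visit and does not fill the gap.

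On the wait, the 24-hour bullet is the operative rule and the 48-hour text sits in a descriptive comparison. That is fair, but the comparison is with another centre's regimen and is not a log of superseded text. It states what this protocol does, so both figures are current.

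On G.2, a reader might infer that an infant steady at 9 or 10 receives contradictory orders. The documents do not support that. An infant whose dose is raised has not been weaned, so both rules can be obeyed, and G.2 applies only when comfort measures have failed. Two consecutive scores above 8 is also the trigger for starting methadone and, in section E, for restarting it. A short-interval trigger beside a daily average is therefore the protocol's usual pattern. What remains is narrower. The middle band is described as observation, the physician pathway is discretionary and puts no number on severe, G.2's increase is mandatory, and nothing says how the three fit together.

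**Conclusion.** The monitoring inconsistency holds and is the point to act on. Between 48 and 72 hours off methadone, the scoring that section E's rules need is not scheduled: a nominal 6 to 8 remote scorings are absent, leaving 2 scheduled scores, or 0 to 1, for that day. This assumes that total weaning and discontinuation both mean the last dose; the documents give no other definition. The 24-versus-48-hour wait also holds, as a plain mismatch. G.2 needs clarification only.

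A reader might go on to infer an effect on length of stay or readmission, or conclude that the effect on length of stay must be small because discharge already requires 72 hours without re-escalation. Neither can be derived. The documents give no rate of re-escalation or rebound. Discharge also requires at least 3 days of successful weaning, and the text does not say whether a day on hold counts towards those 3 days.

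**What to change.** 1. Change 48 to 72 hours in Schedule of Events footnotes b and c and in services items f and h, to match section E. Section E already requires the visits. The added burden is up to 6 to 8 teleconferences per infant, so 25 × 6 = 150 to 25 × 8 = 200 over the planned 25 infants.
2. Have the clinical team choose one wait before weaning resumes after a Table 2 re-escalation, and put it in both the escalation bullet and item 3 of the differences list.
3. Add a sentence to G.2 and to Table 2 saying that two consecutive scores above 8 despite comfort measures is an acute trigger at home, applying alongside the 24-hour-average rule. State how it relates to the physician pathway.

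Beyond the calls, the cost is amendment wording and a notice to NICU and home-care staff. Sample size and analysis are unaffected.

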- 3) Observe a 48-hour (instead of 24) of stable scores prior to initial weaning and prior to wean after re-escalation if patient falls in table 2.

C. Discharge home:

Infants will be discharged home or to Operation PAR when they are deemed stable by the treating team.

Principal Investigator: [name], MPH

Application Number: IRB00107690

Stability is defined as:

- 1) A maximal dose of methadone of ≤ 0.04 mg/kg at the time of discharge (Step 4 of Table 2), and
- 2) A history of successful weaning of methadone for a least 3 days prior to discharge, and
- 3) No dose re-escalation in the previous 72 hours prior to discharge.

Timing of medication administration may be changed gradually prior to discharge, as allowed by hospital policy, to accommodate outpatient administration by Kids Home Care.

Weaning at home will follow the weaning protocol delineated above. Finnegan scoring will be continued at home. It will be done twice daily by the visiting Kids Home Care RN. Virtual Finnegan scoring assessment will be done as described above every 3 to 4 hours by teleconferencing with the Kids Home Care RN versed in the care of infants with NAS.

D. Discontinuation of methadone:

Methadone will be discontinued when the dose is 0.01 mg/kg/dose every 24 hours and the previous 24-hour average if ≤ 6 .

E. Home observation post discontinuation of methadone:

Observe infant for 72 hours off medication with twice daily nursing visits. Treatment is considered successful if infant's 24-hour average remains < 8 .

This observation period is important as it allows to watch for possible rebound of symptomatology after cessation of medical intervention, and is in accordance with the standard of care that infants with NAS receive at JHACH. If during this observation period infants develop rebound symptomatology (defined as a 24 hour Finnegan score average of > 8), the nurse will institute appropriate measures of comforting infant and reducing / eliminating noxious stimuli. If comfort measures fail and Finnegan scores remain > 8 on 2 consecutive assessments performed at 3-4 hour intervals, methadone will be resumed at the last dose that infant received prior to discontinuation. Further Re-escalation and weaning will be performed per initial protocol.

F. Pediatrician Follow-up:

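### For a home infant with consecutive re-escalations, a 24-hour Finnegan value above 6 and below 8 means resume weaning under Table 2 but re-admit under G.2, and at Step 8 the same interval has no stated action

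*Combined protocol and SAP*

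**What the plan says.** **Weaning.** In the Demonstration Study Methadone Protocol, Table 2 starts the taper with "wean after 48 hours of stable scores (i.e. 2 consecutive 24 hour Finnegan score averages < 8" and continues it with "Wean to the next step if the 24 hour Finnegan score average is < 8". An average of 8 to 10 means hold, and 11 or more means escalate. Under Table 2 Escalation, an infant who has been stepped back up is handled by "Weaning will resume after 24 hours of stable scores (i.e. a 24 hour average of <8". Section C (Discharge home) carries all of this outside the hospital: "Weaning at home will follow the weaning protocol delineated above".

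**Re-admission.** Section G.2 first says that two consecutive scores above 8 during the wean, despite comfort measures, lead to a return to the previous effective dose. It then gives the rule "consecutive re-escalation of medication with no control of symptoms (i.e. 24 hour Finnegan scores > 6), such infant will be re-admitted". Two bullets follow. An infant discharged below 0.04 mg/kg is re-admitted if consecutive re-escalations bring the dose to 0.05 mg/kg. An infant discharged at 0.04 mg/kg may go up two increments, to 0.07 mg/kg, before re-admission. Neither bullet contains a score threshold. A re-admitted infant is off-treatment and has no further home nursing visits.

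**End of treatment.** Step 8 (0.01 mg/kg every 24 hours) is the last row of Table 2. Section D says "Methadone will be discontinued when the dose is 0.01 mg/kg/dose every 24 hours and the previous 24-hour average if ≤ 6". For the observation period off the drug, section E says "Treatment is considered successful if infant's 24-hour average remains < 8".

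**Analysis.** Section 6 (Study Statistics) compares the proportion re-admitted within 30 days between groups by a chi-squared or Fisher's exact test. Secondary objective 3 concerns re-admission for NAS-related reasons. The planned size is 25 dyads per group, and General Design Issues describes the study as non-randomized and un-blinded.

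**The concern.** Re-admission is both a tested outcome and a change of treatment status. Here the plan offers more than one rule for it, and the rules disagree for scores in the range that Table 2 calls stable. Two clinicians could each follow the document to the letter, one weaning the infant and the other bringing it back to hospital.

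The ambiguity falls on one group only. The opening section of the plan says infants have historically stayed in hospital until narcotics are fully weaned, so the home-weaning rules govern the methadone group alone. With open treatment, the choice between rules lies with staff who know the assignment. A difference in re-admission rates could then partly reflect which passage was consulted.

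The lower end of the taper has a related gap. An infant at Step 8 with an average just above 6 has no instruction that applies, so the duration of the last step is left to whoever is deciding.

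**Working it through.** The plan states no figure to reproduce on this point, so the check applies each rule as written to the same score.

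**Step 1: rules side by side.** The G.2 column assumes an infant who requires consecutive re-escalation and reads the G.2 value as a 24-hour average.

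| 24-hour average | Table 2 | G.2 sentence | D, at Step 8 | E, off drug |
|---|---|---|---|---|
| 6 | wean | controlled | stop | success |
| 6.5 | wean | re-admit | do not stop | success |
| 7 | wean | re-admit | do not stop | success |
| 7.5 | wean | re-admit | do not stop | success |
| 8.5 | hold | re-admit | do not stop | rebound |
| 11 | escalate | re-admit | do not stop | rebound |

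At 6 or below, Table 2, G.2 and D agree. Above 6 and below 8, Table 2 and the G.2 sentence give opposite instructions.

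**Step 2: the averages affected.** Scores are taken every 3 to 4 hours, which is 8 or 6 per day, and are assumed to be whole numbers.
- Six scores: daily totals 37 to 47, so averages 37/6 = 6.17 to 47/6 = 7.83.
- Eight scores: daily totals 49 to 63, so averages 49/8 = 6.125 to 63/8 = 7.875.

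**Step 3: the bullets.** Section C allows discharge only at 0.04 mg/kg or less, so the two bullets together cover every infant sent home under it. As an illustration, take an infant discharged at Step 4 (0.04), weaned to Step 6 (0.02), then stepped back twice in succession to Step 5 (0.03) and Step 4 (0.04), and now averaging 7.
- Table 2: resume weaning.
- G.2 sentence: re-admit.
- G.2 bullet: 0.04 is below 0.07, so re-admission is not yet due.

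**Step 4: scores or average.** The G.2 sentence speaks of 24-hour scores, whereas Table 2 speaks of the average. The two measures can differ in the same infant. Six illustrative scores of 9, 9, 6, 6, 6, 6 contain two consecutive values above 8, so G.2 calls for a step back up. Their average is 42/6 = 7, so Table 2 calls for a wean.

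**Step 5: Step 8.** With an average above 6 and below 8:
- the wean criterion is met, but no lower step is listed;
- D's stop criterion (6 or below) is not met;
- the hold rule (8 to 10) and the escalation rule (11 or more) do not apply.

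No rule states an action.

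**Step 6: effect on the outcome.** One re-admission in 25 infants is 1/25 = 4 percentage points. The step is larger if only infants sent home on methadone form the denominator. The Background section costs 10 days of home care, so re-admissions during the home taper would ordinarily fall within the 30 days.

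**The case against.** The best defence is that the G.2 sentence applies only to an infant who still needs repeated re-escalation. Escalation is triggered by an average of 11 or more (Table 2) or by two consecutive scores above 8 (G.2), so an infant who has settled at 7 arguably no longer qualifies. The bullets can also be read as the working rule, with the figure of 6 as a loose gloss. At Step 8, Table 2 gives only a minimum number of doses, so remaining there is allowed. What is missing may be a single sentence saying so.

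Much of this stands. The precondition is real: **a reader might infer that an average of about 7 is enough to re-admit, and the documents do not say that**.

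The defence does not remove the conflict. On Table 2's trigger, an infant averaging 11 or more already exceeds 6, so the gloss would add nothing. On G.2's own trigger, the example in Step 4 of the working shows that an infant can call for re-escalation and still average 7. Reading the bullets as the whole rule is possible, but the text does not say that they replace the sentence.

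On Step 8, a reader might also infer that D contradicts Table 2. It does not. A stricter criterion for stopping than for stepping down is a legitimate choice, and D is the only explicit stop rule. The fault there is a missing instruction, alongside a different cut-off in E for success off the drug.

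**Conclusion.** The point holds in a limited form. Given consecutive re-escalation at home, values above 6 and below 8 lead to weaning under Table 2 and to re-admission under the G.2 sentence, while the G.2 bullets decide by dose alone. Off-treatment status follows from whichever is used. Each re-admission that depends on the passage chosen moves the methadone group's rate by 4 percentage points, taking all 25 infants as the denominator. The documents give no basis for predicting how many infants this would affect. The conclusion rests on reading G.2's scores as comparable with the 24-hour average, which is reasonable but not explicit. The Step 8 gap is separate and is an omission.

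Two further inferences are tempting and unsupported.
- **G.1 against G.2.** G.1 uses "uncontrolled NAS symptoms (defined as a 24-hour Finnegan score average ≥ 11" and G.2 uses above 6, which might look like rival definitions. G.1 governs adding second-line therapy at maximal dosing (0.1 mg/kg every 4 hours). G.2 governs return from home, at the much lower doses named in its bullets. The two rules decide different actions, so the gap between their cut-offs measures no conflict.
- **An effect on mean length of stay.** Someone might apply the plan's 20-40% needing second-line therapy to the 25 and attribute extra Step 8 days to them. The Accrual text describes the infants counted as moving to home care and already allows for that percentage. No figure is given for time spent at Step 8. No estimate of lengthened stay can be derived.

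**What to change.** The investigators should reconcile the G.2 sentence, the two G.2 bullets and Table 2 into one re-admission rule. It should state whether score, dose or both decide, and whether score means single values or the 24-hour average. They should also state the action at Step 8 when the wean criterion is met and the discontinuation criterion is not. Which thresholds to use is a matter for the clinical team, and none is proposed here.

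At each re-admission and at each discontinuation, record the 24-hour average, the current dose and the rule invoked. If any infants were managed before the wording is settled, report how many re-admissions would change under each reading.

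The cost is a wording amendment and a few case report form fields. Scores are already collected every 3 to 4 hours at home, so no visits or assessments are added.

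### The home re-admission provisions disagree with one another once an infant has begun weaning at home, so the same course can be classed as re-admission or as continued home treatment

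*Combined protocol and SAP*

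**What the plan says.** Section C (Discharge home) allows discharge on methadone at no more than 0.04 mg/kg, which is Step 4 of Table 2, and states that weaning continues at home on the same protocol. Under Table 2 Escalation, "Escalation will take place by going back one step in the dosing regimen". The relevant rows of Table 2 are "Step 2 0.07 Q12 h 2", then "Step 3 0.05 Q12 h 2", then "Step 4 0.04 Q12 h 2" and lastly "Step 5 0.03 Q12 h 2" (dose in mg/kg, interval, minimum number of doses). Below them come 0.02 Q12h (Step 6), 0.01 Q12h (Step 7) and 0.01 Q24h (Step 8).

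Section G.2 (Re-admission to the JHACH NICU) then contains four provisions:

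- On two consecutive scores above 8 during weaning, despite comfort measures, the dose returns to the last one that controlled symptoms.
- An infant who needs consecutive re-escalation without control of symptoms is re-admitted. No dose is named. This is called the general sentence below.
- Where the discharge dose was below 0.04 mg/kg, the provision reads: "such infant will be re-admitted to the hospital if consecutive re-escalation of methadone are required and infant reaches a dose of 0.05 mg/kg".
- Where the discharge dose was 0.04 mg/kg and the infant does not tolerate weaning at home and needs escalation, it reads: "the dose will be increased in 2 increments per protocol to a value of 0.07 mg/kg before re-admission to the hospital".

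A re-admitted infant is off-treatment, cannot later go home on methadone, and has no further home nursing visits.

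**The concern.** The provision for infants discharged at 0.04 mg/kg fixes both a number of increments and an end dose. It is written for infants who fail weaning at home, and many of these will already be below 0.04 when they fail. For them the two halves point to different places. The general sentence gives a third instruction, and the text does not say whether the two dose limits qualify it or add to it.

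This is the boundary between home and hospital care, and home-care nurses work to it outside the hospital. It also generates data. Re-admission decides off-treatment status, and Section 6 compares readmission within 30 days between the groups by a chi-squared or Fisher's exact test, in support of the objective on safe transition to home. The rule acts only in the methadone group. If two teams can read it differently for the same infant, part of that outcome reflects the reading and not the infant.

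**Working it through.** **Inputs.** The Table 2 ladder, upward from the lowest step: 0.01 Q24h, 0.01 Q12h, 0.02, 0.03, 0.04, 0.05, 0.07 (the last five all Q12h). One increment is one step back (Table 2 Escalation). The limits are 0.05 and 0.07 mg/kg (Section G.2).

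**The plan's own figure.** 0.04 → 0.05 → 0.07 is two steps. The stated two increments to 0.07 therefore reproduce exactly from 0.04, and both limits are listed steps (0.05 is Step 3, 0.07 is Step 2).

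**After home weaning, for an infant discharged at 0.04:**

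| Current dose | Two increments end at | Steps needed to reach 0.07 |
|---|---|---|
| 0.04 | 0.07 | 2 |
| 0.03 | 0.05 | 3 |
| 0.02 | 0.04 | 4 |
| 0.01 Q12h | 0.03 | 5 |
| 0.01 Q24h | 0.02 | 6 |

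The two halves agree only in the first row.

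**The general sentence against the limits.** Take consecutive re-escalation to mean two in a row (an assumption, since the text gives no count), with symptoms uncontrolled throughout.

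- Discharged at 0.04, weaned to 0.03: the path is 0.03 → 0.04 → 0.05. The general sentence re-admits at 0.05. If increments are counted from 0.04, only one has been used and the infant can go on to 0.07 first. If they are counted from 0.03, both have been used but 0.07 has not been reached.
- Discharged at 0.02: the path is 0.02 → 0.03 → 0.04. The general sentence re-admits at 0.04. The limit for this group, 0.05, is three steps away and has not been met.
- Discharged at 0.03 and not weaned further: the path is 0.03 → 0.04 → 0.05. Both provisions are met at 0.05, so here they agree.

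**Same current dose, different action.** Two infants are on 0.03 at home, one discharged at 0.03 and the other discharged at 0.04 and since weaned. Both re-escalate to 0.04 and then 0.05. At 0.05 the first meets its re-admission limit, while the second may remain at home up to the 0.07 limit. Section G.2 gives no reason for the difference. It also does not say whether 0.07 may be given at home or whether reaching it triggers re-admission.

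**Scale.** With 25 methadone infants, one infant classed differently moves the re-admission proportion by 1/25 = 4 percentage points. This is the weight of one infant, not an estimated effect.

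**The case against.** The strongest reply is that Section G.2 first returns an infant who fails weaning to the last dose that controlled symptoms. An infant discharged at 0.04 who fails at 0.03 goes back to 0.04. The provision can then be read as governing increases above the discharge dose, 0.05 and then 0.07, and its two halves agree. That reading is possible, but the text does not state it. Nor is the last controlling dose always the discharge dose: an infant who weaned from 0.04 through 0.03 and failed at 0.02 would return to 0.03. Even where the reading works, 0.03 → 0.04 → 0.05 without control is consecutive re-escalation, which the general sentence re-admits and the dose limit keeps at home.

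Two further points on the other side stand in full. First, a reader might infer that the limits do not fit Table 2. They do: both are listed steps, and 0.04 to 0.07 is exactly two. Second, a reader might infer that the higher limit gives the earliest discharges more leeway and makes early discharge look safer. The documents do not support this:

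- Only the absolute ceiling is higher. Steps from discharge dose to limit are 2 from 0.04, 2 from 0.03, 3 from 0.02, and 4 and 5 from the two 0.01 steps.
- If 0.07 may be given at home while 0.05 triggers re-admission, the 0.04 group has 2 tolerated steps against 1, 2, 3 and 4. It exceeds only the 0.03 group.
- Discharge dose does not fix length of stay. An infant who passed through Steps 1A to 1C can leave on 0.04 later than an uncomplicated infant leaves on 0.03.
- Readmission is compared between treatment groups, not by discharge dose.

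Nor are the two infants at 0.05 identical. They share a current dose, but one is one step above its discharge dose and the other is two.

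**Conclusion.** The point holds as an internal contradiction. Once home weaning has begun, two increments and 0.07 mg/kg no longer describe the same limit (0.05 against 0.07 from a current dose of 0.03, and 0.04 against 0.07 from 0.02). The general sentence can call for re-admission before either dose limit. Infants on the same current dose are treated differently at 0.05 by discharge dose, without a stated reason.

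The step counts rest only on Table 2 and its one-step rule. The conflict with the general sentence rests on reading consecutive as two in a row. The size and direction of any effect on the readmission comparison are not known, because the documents do not say how many infants will leave on 0.04 or reach 0.05 at home. The case for correction is that a home safety boundary, off-treatment status and a tested outcome all depend on text that can be read in more than one way. It does not rest on a demonstrated bias.

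**What to change.** Reconcile the general sentence, the two dose limits in Section G.2 and Table 2 so that together they give one consistent instruction. The text should make clear:

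- where increments are counted from once an infant has weaned at home;
- whether the limit dose is given at home or itself triggers re-admission;
- how the general sentence relates to the dose limits;
- the reason for any difference by discharge dose.

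The content is for the clinical team, and no limit or rule is proposed here. In the analysis, list each re-admission with the discharge dose and the Table 2 step at re-admission, so that a reader can see which provision applied.

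The cost is a short protocol amendment, retraining of the home-care nurses and one additional listing.
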